2.4.5.4 Analyses of vital sign variables

The summary statistics (including number, mean, median, Q1, Q3, standard deviation, minimum and maximum) of all vital signs variables (raw data and changes from baseline) will be calculated for each visit or study assessment (baseline, each postbaseline time point, last on-treatment and/or minimum and maximum value during the treatment-emergent adverse event period) by treatment group. For blood pressure, height and weight, mean changes from baseline with the corresponding standard error will be plotted over time (at same time points) in each treatment group.

PCSA will be assessed based on age group at each visit. After subjects turn to be adult, the adult criteria will be applied. The incidence of PCSAs at any time during the treatment-emergent adverse event period will be summarized by treatment group irrespective of the baseline level and/or according to the following baseline status categories:

- Normal/missing.
- Abnormal according to PCSA criterion or criteria.

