1.6 STATISTICAL MODIFICATIONS MADE IN THE STATISTICAL ANALYSIS PLAN

In this section summarize major changes in statistical analysis features made in approved SAP versions, with emphasis on changes after study start (after the first patient was enrolled).

Statistical analysis for open-label period was not addressed in previous version of SAP or in amended protocol. The statistical analysis plan history table below gives the timing, rationale, and key details for major changes to the statistical analysis features in the statistical analysis plan. Changes also incorporated in a protocol amendment are cross-referenced to [Table 3](#).

Table 3 - Statistical analysis plan statistical changes

SAP version number	Date approved	Rationale	Description of statistical changes
1	05-May-2019	Many of the patients will be studied during the period of age-expected brain volume increase, thus brain atrophy is not appropriate	Replace "brain atrophy" to "percentage change of brain volume".
1	05-May-2019	To explore long-term treatment effect in teriflunomide/teriflunomide and placebo/teriflunomide group	Add annualized relapse rate (ARR) and time to sustained disability progression as additional endpoint in section 2.1.3.3 and 2.4.4.3.
2		To fulfill requirement from health authorities	Added ethnicity in the demographic section
2		To investigate Covid-19 impact on study conduct and assessment of safety and efficacy of teriflunomide	1) Added Covid-19 related disposition summary 2) Added extent of exposure and compliance summary for Covid-19 impact. 3) Added Covid-19 related adverse event analysis. 3) Modified censoring rule for time-to-event endpoint and OL EOT analysis visit window for potential Covid-19 delay.
2		To correct typo	Added 1 day for each of the target day and analysis visit windows in section 2.5.3

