2.1.4.4 Vital signs variables

Vital signs include: radial heart rate, systolic and diastolic blood pressure (standing and supine) and body temperature. Weight and height will be documented in the growth charts.

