2.4.5 Analyses of safety data

The summary of safety results will be presented by treatment patients actually received in the double-blind and open-label period (placebo/teriflunomide and teriflunomide/teriflunomide) and overall treatment group. Baseline values of the double-blind period will be used as the baseline in the safety analysis for the open-label CSR, unless otherwise noted.

General common rules

All safety analyses will be performed on the safety population as defined in [Section 2.3.3](#), unless otherwise specified, using the following common rules:

- Safety data in patients who do not belong to the safety population will be listed separately.
- The baseline value is defined as the last available value before the first intake of IMP in the double-blind period.
- The potentially clinically significant abnormality (PCSA) values are defined as abnormal values considered medically important by the Sponsor according to predefined criteria/thresholds based on literature review and defined by the Sponsor for clinical laboratory tests, vital signs, and ECG (PCSA version dated May 2014 [[Appendix A](#)]).
- PCSA criteria will determine which patients had at least 1 PCSA during the treatment-emergent adverse event period, taking into account all evaluations performed during the treatment-emergent adverse event period, including nonscheduled or repeated evaluations. The number of all such patients will be the numerator for the on-treatment PCSA percentage.
- The treatment-emergent PCSA denominator by group for a given parameter will be based on the number of patients assessed for that given parameter in the treatment-emergent adverse event period by treatment group on the safety population.
- For quantitative safety parameters based on central laboratory/reading measurements, descriptive statistics will be used to summarize results and change from baseline values of the double-blind period by visit and treatment group. Summaries will include the endpoint value and/or the minimum and maximum value. The endpoint value is commonly defined as the value collected at the same day/time of the last administration of IMP in the open-label period. If this value is missing, this endpoint value will be the closest value prior to the last dose intake.

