	24 months/2 years to <6 years old (Children)	<22 per minutes >34 per minutes	
	6 to <12 years old (Children)	<18 per minutes >30 per minutes	
	12 to 16/18 years old (Adolescents)	<12 per minutes >20 per minutes	
SaO2	All age ranges	\leq 95%	
Weight	All ranges	\geq 5% weight loss from baseline	Based on identification of trends in the child's growth with a series of visits WHO Multicentre Reference Study Group, 2006; Center for Disease Control. Growth chart 2007

**Criteria for potentially clinically significant abnormalities
For studies in children
(Version 3.0 May 2014)**

Parameter	Age range	PCSA	Comments
Clinical Chemistry			
ALT/SGPT	All age ranges	>3 ULN By distribution analysis: >3 ULN >5 ULN >10 ULN >20 ULN	Ref Molleston JP et al. JPGN 2011; Moritz et al., Pediatrics 1999; Moritz et al., Pediatr Nephrol 2005 ; Sedlacek et al., Seminars in Dialysis 2006) Gong G et al. Clinical Biochemistry 2009; Masilamani et al. Arch Dis Children 2012; Mulberg AE et al. Pediatric Drug Development Concepts and applications. John Wiley & sons, Inc. 2009 Based on normal ranges: 6 to 50 U/L (0-5 days), 5 to 45 U/L (1-19 years)
AST/SGOT	All age ranges	>3 ULN By distribution analysis: >3 ULN >5 ULN >10 ULN >20 ULN	Based on normal ranges: 35 to 140 U/L (0-5 days), 15 to 55 U/L (1-9 years), 5 to 45 U/L (10-19 years)
Alkaline Phosphatase	All age ranges	≥1.5 ULN	Based on normal ranges: 145 to 420 U/L (1-9 years), 130 to 560 U/L (10-11 years), 200 to 495 U/L (Boys 12-13 years), 105 to 420 U/L (Girls 12-13 years), 130 to 525 U/L (Boys 14-15 years), 70 to 130 U/L (Girls 14-15 years), 65 to 260 U/L (Boys 16-19 years), 50 to 130 U/L (Girls 16-19 years)
Total Bilirubin	All age ranges	≥1.3 ULN	CF = mg x 1.7 = μmol Based on normal ranges: <6 mg/dL (Term 0-1 day), <8 mg/dL (Term 1-2 days), <12 mg/dL (Term 3-5 days), <1 mg/dL (Term >5 days)
Conjugated Bilirubin	All age ranges	>35% Total Bilirubin and TBILI≥1.3 ULN	CF = mg x 1.7 = μmol Based on normal range: 0 to 0.4 mg/dL

**Criteria for potentially clinically significant abnormalities
For studies in children
(Version 3.0 May 2014)**

Parameter	Age range	PCSA	Comments
ALT and Total Bilirubin	All age ranges	ALT ≥3 ULN and Total Bilirubin ≥2 ULN	
CPK	All age ranges	≥3 ULN	
Creatinine	Birth/0 to <6 years old (Neonates, Infants, Children)	>53 µmol/L or 0.6 mg/dL	CF = mg x 8.8 = µmol Based on normal ranges: <0.6 mg/dL (0-1 year), 0.5 to 1.5 mg/dL (1 to 16/18 years)
	6 years to <12 years old (Children)	>90 µmol/L or 1.1mg/dL	

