(Version 3.0 May 2014)**

Parameter	PCSA	Comments
Neutrophils	<1.5 GIGA/L (Non-Black); <1.0 GIGA/L (Black)	International Consensus meeting on drug-induced blood cytopenias, 1991. FDA criteria.
Monocytes	>0.7 GIGA/L	
Basophils	>0.1 GIGA/L	
Eosinophils	>0.5 GIGA/L or >ULN (if ULN ≥ 0.5 GIGA/L)	Harrison- Principles of internal Medicine 17th Ed., 2008.
Hemoglobin	≤115 g/L (Male); ≤95 g/L (Female) ≥185 g/L (Male); ≥165 g/L (Female) Decrease from Baseline ≥20 g/L	Criteria based upon decrease from baseline are more relevant than based on absolute value. Other categories for decrease from baseline can be used (≥30 g/L, ≥40 g/L, ≥50 g/L).
Hematocrit	≤0.37 v/v (Male) ; ≤0.32 v/v (Female) ≥0.55 v/v (Male) ; ≥0.5 v/v (Female)	
RBC	≥6 Tera/L	Unless specifically required for particular drug development, the analysis is redundant with that of Hb. Otherwise, consider FDA criteria.
Platelets	<100 GIGA/L ≥700 GIGA/L	International Consensus meeting on drug-induced blood cytopenias, 1991.
Urinalysis		
pH	≤4.6 ≥8	
Vital signs		
HR	≤50 bpm and decrease from baseline ≥20 bpm ≥120 bpm and increase from baseline ≥20 bpm	To be applied for all positions (including missing) except STANDING.

**Criteria for potentially clinically significant abnormalities
for Phase 2/3 studies (oncology excepted)
(Version 3.0 May 2014)**

Parameter	PCSA	Comments
SBP	≤95 mmHg and decrease from baseline ≥20mmHg ≥160 mmHg and increase from baseline ≥20 mmHg	To be applied for all positions (including missing) except STANDING.
DBP	≤45 mmHg and decrease from baseline ≥10 mmHg ≥110 mmHg and increase from baseline ≥10 mmHg	To be applied for all positions (including missing) except STANDING.
Orthostatic Hypotension		
Orthostatic SDB		
Orthostatic DBP	≤-20 mmHg ≤-10 mmHg	
Weight	≥5% increase from baseline ≥5% decrease from baseline	FDA Feb 2007.
ECG		Ref.: ICH E14 guidance (2005) and E14 Q&A (2012), and Cardiac Safety Research Consortium White Paper on PR and QRS (Nada et al. Am Heart J. 2013; 165(4) : 489-500)
HR	<50 bpm <50 bpm and decrease from baseline ≥20 bpm <40 bpm <40 bpm and decrease from baseline ≥20 bpm <30 bpm <30 bpm and decrease from baseline ≥20 bpm >90 bpm >90 bpm and increase from baseline ≥20bpm >100 bpm >100 bpm and increase from baseline ≥20bpm >120 bpm >120 bpm and increase from baseline ≥20 bpm	Categories are cumulative Categories are cumulative

**Criteria for potentially clinically significant abnormalities
for Phase 2/3 studies (oncology excepted)
(Version 3.0 May 2014)**

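### The open-label SAP plans no age- and sex-standardised growth analysis, so no planned table separates slow or absent growth from normal growth in patients under 18

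*SAP*

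**What the plan says.** - **Summaries.** SAP 2.4.5.4 gives descriptive statistics of "all vital signs variables (raw data and changes from baseline) will be calculated for each visit or study assessment", by treatment group. For the figures it adds: "For blood pressure, height and weight, mean changes from baseline with the corresponding standard error will be plotted over time".
- **Baseline.** SAP 2.4.5: "The baseline value is defined as the last available value before the first intake of IMP in the double-blind period". SAP 2.1.1 also describes weight, height and BMI at an extension baseline, but only as a patient characteristic. Change is not measured from it.
- **Paediatric criterion.** Appendix A flags a weight change of at least "5% weight loss from baseline", for all age ranges. The comment beside it reads: "Based on identification of trends in the child's growth with a series of visits". No criterion for height is listed.
- **Adult criterion.** SAP 2.4.5.4 switches to the adult criteria once a patient becomes adult. For weight these are "≥5% increase from baseline ≥5% decrease from baseline".
- **Growth charts.** SAP 2.1.4.4: "Weight and height will be documented in the growth charts". No analysis of the charts is specified.
- **Subgroups.** SAP Appendix B plans none for vital signs, so height and weight are not split by age, sex or pubertal status.
- **Time scale.** SAP 2.5.3 counts open-label visit days from the first open-label dose.

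**The concern.** Patients are 10 to 17 years old at entry and can be followed for up to 192 weeks. Most will gain height and weight in that time, by amounts that depend on age, sex and pubertal stage. A raw mean change rises whether growth is normal or slowed, and both open-label groups take teriflunomide, so there is no concurrent untreated reference.

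The paediatric weight flag does not fill the gap. Appendix A says it rests on growth trends over a series of visits, but the rule is a single fixed loss from one old value. In the same appendix, the paediatric blood pressure limits are age-banded and rest on percentiles for sex, age and height. Height and weight have no such reference.

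What is at stake is how the open-label report can be read. A rising curve and a near-empty weight table could be taken as reassurance on growth when neither can separate slow growth from normal growth.

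**Working it through.** The documents give no expected growth rate. Growth figures below are labelled assumptions.

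**1. Age of the baseline.** The protocol and SAP cap time since randomization at 192 weeks. The flow-chart notes state a maximum open-label duration of 184 weeks. This reproduces as the cap less the 8-week PK run-in: 192 − 8 = 184. At the last open-label visit the baseline can be 192 × 7 / 365.25 = 3.68 years old.

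**2. Reach of the paediatric weight flag.** Let g be the fractional gain since baseline. The flag fires at 0.95 × baseline weight, so the fall needed from current weight is 1 − 0.95/(1 + g).

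| Gain since baseline (assumed) | Fall from current weight needed |
|---|---|
| 0% | 5.0% |
| 10% | 13.6% |
| 20% | 20.8% |
| 30% | 26.9% |
| 50% | 36.7% |

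Example (assumed weights): a child of 30 kg at baseline who reaches 45 kg is flagged only at 0.95 × 30 = 28.5 kg or less. A child who stays at 30 kg for 192 weeks has a change of 0% and is never flagged.

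**3. Adult flag on the same baseline.** A patient of 50 kg at enrolment (assumed) is flagged at 50 × 1.05 = 52.5 kg once adult. The rule does not distinguish this from normal adolescent weight gain.

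**4. What a raw height curve shows.** Assume 5 cm/year (range 2 to 7) and a 30% slowing over 2 years. Normal growth gives 5 × 2 = 10.0 cm (4.0 to 14.0). Slowed growth gives 10.0 × 0.7 = 7.0 cm (2.8 to 9.8). Both plot as rising curves, and the two ranges overlap.

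**5. Mixed elapsed time.** A patient can enter the open-label period from about Week 8 to Week 96. At open-label Week 48, time since baseline therefore runs from 8 + 48 = 56 weeks to 96 + 48 = 144 weeks. At the assumed 5 cm/year, normal growth alone gives 5 × 56 × 7 / 365.25 = 5.4 cm to 5 × 144 × 7 / 365.25 = 13.8 cm at the same plotted visit.

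This mixing need not be equal between groups. The sample-size section assumes relapse by 2 years in 60% on placebo and 36.8% on teriflunomide. If that held, former placebo patients would tend to switch earlier and show smaller raw gains at a given open-label visit. That could hide slower growth in the teriflunomide/teriflunomide group.

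**The case against.** **A reader might infer that growth faltering cannot be seen at all.** The documents do not support that. SAP 2.4.5.4 gives medians, quartiles, minima and maxima by visit, height and weight go into individual growth charts, and SAP 2.4.5.6 analyses Tanner stage by gender, with time to stage increase and a shift table. Gross faltering could show there. What is missing is a planned table that separates slow growth from normal growth.

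**A reader might infer that the weight flag is loss-only throughout.** It is so only under the paediatric criteria. The adult rule works in both directions.

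**A reader might call growth a main safety question of this trial.** It is in no stated objective and is not a listed adverse event of special interest. The juvenile rat studies described in protocol 3.1.2.3 found no adverse effect on growth. The open-label data are described as supportive and the safety analysis as descriptive. This limits the weight of the point.

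**A reader might see a double standard with brain volume**, because SAP 1.6 notes that "Many of the patients will be studied during the period of age-expected brain volume increase". The comparison is weak. SAP 2.4.4.2.3 summarises brain volume change in its original scale, so brain volume is not age-standardised either.

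**The double-blind baseline can be defended.** It is the last pre-treatment value and a natural anchor for long-term change. Its age alone is not the defect. The difficulty is raw change from it, without reference to age or elapsed time.

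**Randomization was stratified by pubertal status**, and age, gender and Tanner stage are tabulated by group. This reduces concern about age and sex mix, but it does not address differing times of entry into the open-label period.

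**Conclusion.** The point holds as a low-cost improvement to the open-label SAP. No age- or sex-referenced growth measure is planned, no height criterion exists, and under the paediatric rule a patient with no weight gain for up to 192 weeks is never flagged. The adult rule, on the same baseline, counts normal adolescent weight gain as an abnormality.

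The 192-week and 184-week figures and the 56-to-144-week spread follow from the documents. The table of falls is exact for each assumed gain. The centimetre figures rest on an assumed 2 to 7 cm/year and are illustrative; the defect does not depend on them. Nothing here suggests that growth is in fact impaired.

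The finding does not extend to the double-blind period. Its SAP is a separate document that was not available, so a reader should not infer that standardised growth or a placebo comparison is missing from the whole programme.

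**What to change.** In SAP 2.4.5.4:

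1. Add standard deviation scores for age and sex for height, weight and BMI, from one named growth reference. Appendix A already cites growth references, but the sponsor must confirm that the chosen one covers this trial's ages.
2. Summarise and plot change in score by visit and group, from both the double-blind and the extension baseline, for the ages the reference covers.
3. Keep the existing count of 5% weight loss. Add the number of patients whose height or weight score falls by more than an amount fixed before database lock.

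**Cost.** SAP text and standard programming. Age, sex, height and weight are already collected, and the open-label flow chart schedules height with the vital signs from the transition visit on.

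**Downsides.** One reference is applied across all countries. Height is sparse: in the double-blind period it is taken only at randomization and EOT, that EOT visit need not be done when a patient switches after relapse or high MRI activity, and remote visits collect weight only.

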- a The open label period starts by the transition visit. It is recommended that there is no time gap between the 2 periods, or as short as possible and if possible less than 2 weeks. In case of start of the open label period at the end of the 96 weeks of the double-blind period, the transition visit will generally coincide with the EOT visit of the double-blind period. Recommended windows: The window for obtaining biological samples at any given visit will be  $\pm 7$  days. All other treatment period assessments should be completed within  $\pm 7$  days of the scheduled visit date relative to the transition visit. Post drug elimination follow-up visits should be  $\pm 7$  days of scheduled visit relative to end of treatment.
- b For a regional or national emergency declared by a governmental agency, contingency measures are included in [Section 17.7](#)
- c End-of-treatment and premature discontinuation visit.
- d For patients discontinuing treatment, 2 post drug elimination follow up visits should be scheduled 2 weeks and 4 weeks after study medication discontinuation and initiation of the drug elimination procedure. When applicable patients who prematurely and permanently discontinue study medication will be asked to continue until the planned end of double-blind period (ie, 96 weeks after randomization)
- e Re-consent before starting open-label period and after confirmed MS relapse and when patients turn adults as per local regulations.
- f During the adverse event reporting process, specific questions about pulmonary symptoms and peripheral neuropathy symptoms will be asked. (Patients will be instructed to alert the treating physician of symptoms suggestive of immunodeficiency)
- g Including systolic and diastolic blood pressure, heart rate, body temperature, weight and height; patient standing in bare or stocking feet. Height and weight is to be documented in the growth charts –Blood pressure (BP) and heart rate to be measured in both the supine and the standing positions (measures taken 3 minutes after supine and 3 minutes after standing). A sphygmomanometer with a blood pressure cuff appropriate to the patient's arm girth is used. Of note, during remote visits, only weight will be collected.
- h Tanner stage to be assessed at every 24 weeks and EOT for all patients (until complete sexual maturity).

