Infections were the most frequently reported TEAEs in placebo-controlled studies. A low and similar incidence of serious infections was reported across groups (2.5%, 2.4% and 2.5% in the placebo, 7 mg, and 14 mg groups, respectively). The incidence of infections leading to treatment discontinuation was similar across all groups.

The clinical data collected to date do not suggest an increased risk of severe allergic reactions with the use of teriflunomide

In placebo-controlled studies, BP elevations were more frequent on teriflunomide as compared to placebo. The analysis of BP measurements over the 2-year treatment period in placebo-controlled studies showed a higher mean change from baseline with teriflunomide as compared to placebo. Patients who developed hypertension on teriflunomide treatment were usually well controlled with the introduction of or modification of antihypertensive treatment. This was also true for the experience in the long term extension studies.

There was no clinical evidence for pulmonary toxicity in the available clinical data. Events potentially related to peripheral neuropathy were reported in all treatment groups. A modest increase in uric acid elimination, resulting in a 20% to 30% decrease in mean plasma levels of uric acid, was observed. The uricosuric effect was considered to be most probably due to an increase in renal tubular uric acid elimination. There was no evidence for an increased risk of urolithiasis or any other clinically relevant consequence of this effect.

Non clinical studies conducted with teriflunomide showed embryofetal toxic effects in rats and rabbits.

In clinical studies no structural defects were observed in 30 delivered healthy babies (17 from patients and 13 from female partners of male patients treated with teriflunomide).

Overall, the available safety data suggested that both doses of teriflunomide 7 mg and 14 mg administered in clinical studies in patients with RMS were generally well tolerated with a manageable safety profile.

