Parameter	Age range	PCSA	Comments
Vital Signs			Ref. : Kidney Disease Outcomes Quality Initiatives (KDOQI) Guideline 13; 1996; The fourth report on the diagnosis, evaluation, and treatment of high blood pressure in children and adolescents, Pediatrics 2004; Bowman E & Fraser S Neonatal Handbook 2012; Mulberg AE et al. Pediatric Drug Development Concepts and applications. John Wiley & sons, Inc. 2009; Pediatric respiratory rates http://www.health.ny.gov/
SBP	Birth/0 to 27 days old (Neonates)	≤60 mmHg and decrease from baseline ≥20 mmHg ≥85 mmHg and increase from baseline ≥20 mmHg	Based on definition of Hypertension as average SBP or DBP ≥95th percentile for gender, age, and height on ≥3 occasions
	28 days/1 month to 23 months old (Infants)	≤70 mmHg and decrease from baseline ≥20 mmHg ≥98 mmHg and increase from baseline ≥20 mmHg	
	24 months/2 years to <6 years old (Children)	≤70 mmHg and decrease from baseline ≥20 mmHg ≥101 mmHg and increase from baseline ≥20 mmHg	
	6 to <12 years old (Children)	≤80 mmHg and decrease from baseline ≥20 mmHg ≥108 mmHg and increase from baseline ≥20 mmHg	
	12 to 16/18 years old (Adolescents)	≤90 mmHg and decrease from baseline ≥20 mmHg ≥119 mmHg and increase from baseline ≥20 mmHg	
	DBP	Birth/0 to 27 days old (Neonates)	
DBP	28 days/1 month to 23 months old (Infants)	≤34 mmHg and decrease from baseline ≥10 mmHg ≥54 mmHg and increase from baseline ≥10 mmHg	
	24 months/2 years to <6 years old (Children)	≤34 mmHg and decrease from baseline ≥10 mmHg ≥59 mmHg and increase from baseline ≥10 mmHg	
	6 to <12 years old (Children)	≤48 mmHg and decrease from baseline ≥10 mmHg ≥72 mmHg and increase from baseline ≥10 mmHg	
	12 to 16/18 years old (Adolescents)	≤54 mmHg and decrease from baseline ≥10 mmHg ≥78 mmHg and increase from baseline ≥10 mmHg	

**Criteria for potentially clinically significant abnormalities
For studies in children
(Version 3.0 May 2014)**

Parameter	Age range	PCSA	Comments
Orthostatic hypotension	All age ranges	SBP: St - Su \leq -20 mmHg DBP: St - Su \leq -10 mmHg	
Temperature	All age ranges	Rectal, ear or temporal artery: \geq 100.4°F/38.0°C Oral or pacifier: \geq 99.5°F/37.5°C Axillary or skin infrared: \geq 99°F/37.2°C	Ear temperature not accurate below 6 months of age
Respiratory rate	Birth/0 to 27 days old (Neonates)	<30 per minutes >60 per minutes	Based on normal range
	28 days/1 month to 23 months old (Infants)	<24 per minutes >40 per minutes	

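### In the uncontrolled open-label analysis, raw blood-pressure change and a single-reading limit that ignores sex and height cannot separate growth from a teriflunomide effect, and the limit jumps when a patient becomes adult

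*SAP*

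**What the plan says.** Protocol 3.1.2.2 names the effect in adults: "In placebo-controlled studies, BP elevations were more frequent on teriflunomide as compared to placebo". It adds that mean change over two years was also higher than on placebo. SAP 2.1.4.1 lists hypertension as an adverse event of special interest.

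The supplied SAP covers the open-label period only. Section 2 says the double-blind analysis is in a separate SAP, and section 1.1 calls the open-label data non-controlled and supportive. For blood pressure it plans:

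- **Scale.** Raw values and raw change by visit, and a plot: "For blood pressure, height and weight, mean changes from baseline with the corresponding standard error will be plotted over time" (2.4.5.4).
- **Baseline.** "The baseline value is defined as the last available value before the first intake of IMP in the double-blind period" (2.4.5).
- **Trigger.** A patient counts with at least one PCSA in the treatment-emergent period, unscheduled and repeat readings included (2.4.5).
- **Age handling.** "PCSA will be assessed based on age group at each visit. After subjects turn to be adult, the adult criteria will be applied" (2.4.5.4).
- **Paediatric limits (Appendix A).** For the 12 to 16/18 band, high SBP is "≥119 mmHg and increase from baseline ≥20 mmHg"; high DBP is at least 78 with a rise of at least 10. For 6 to under 12 years the levels are 108 and 72, with the same rises. The comment beside them reads: "Based on definition of Hypertension as average SBP or DBP ≥95th percentile for gender, age, and height on ≥3 occasions".
- **Adult limits (Appendix A).** At least 160 SBP or 110 DBP, with the same rises.

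**The concern.** Blood pressure normally rises through adolescence, and the SAP's own limits rise between its two paediatric bands. Raw change over up to 3.7 years in 10- to 17-year-olds therefore contains growth. Both displayed groups (placebo/teriflunomide and teriflunomide/teriflunomide) receive teriflunomide in the open-label period, so comparing them does not give a growth-only reference.

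The PCSA count has two further weaknesses. Within a band, a short 12-year-old girl and a tall 17-year-old boy face the same limit, and one noisy reading is enough. At adulthood the limit rises so far that flags nearly stop. The long-term safety output on a known effect would then depend partly on growth, measurement noise and how many patients have turned 18.

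**Working it through.** The plan states no expected rate or precision for blood pressure, so there is no figure to reproduce. The check has four steps.

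**1. Steps in the limits (Appendix A).**
- At age 12: SBP 119 − 108 = 11 mmHg; DBP 78 − 72 = 6 mmHg.
- At adulthood: SBP 160 − 119 = 41 mmHg; DBP 110 − 78 = 32 mmHg.

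**2. Time scale.** 192 × 7 / 365.25 = 3.68 years. Taking 18 as adulthood (the top paediatric band is labelled 16/18, so this is an assumption), anyone aged 18 − 3.68 = 14.3 years or more at randomization reaches it within 192 weeks. A natural rise of 1 to 2 mmHg/year, assumed, would give a mean change of 3.7 to 7.4 mmHg by then with no drug effect.

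**3. Share ever flagged for high SBP with no drug effect.** Rule: at least one of ten readings with SBP ≥119 and (reading − baseline) ≥20. Ten is the number of scheduled open-label vital-sign visits for a double-blind completer (Weeks 4, 8, 12, then every 12 weeks to 96). The documents give no distributions, so these inputs are assumed: baseline mean 110, between-patient SD 9, within-patient SD 6 or 8 (also applied to the baseline reading), and a linear rise of 0 to 11 mmHg over the ten visits. There were 200,000 simulated patients per scenario. The adult switch assumes age uniform from 12 to under 18 at randomization and open-label entry at Week 96.

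| Within-patient SD | Rise (mmHg) | Paediatric limit throughout | With adult switch |
|---|---|---|---|
| 6 | 0 | 4% | 2% |
| 6 | 4 | 8% | 5% |
| 6 | 8 | 17% | 9% |
| 6 | 11 | 27% | 13% |
| 8 | 0 | 15% | 9% |
| 8 | 4 | 23% | 13% |
| 8 | 8 | 33% | 18% |
| 8 | 11 | 42% | 22% |

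The zero-rise rows are pure reading noise. Growth adds only the difference from them. Requiring three or more qualifying readings under the paediatric limit cuts its column to 0.3–5.0% (SD 6) and 2.1–11.8% (SD 8). Under the adult limit alone, at most 0.2% are flagged in any row.

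**4. Can growth be told from a drug effect?** A second simulation used other assumptions: mean 108 or 112, between-patient SD 8, within-patient SD 8, rise per year counted from randomization, paediatric limit throughout.
- 1 mmHg/year, no drug effect: 23–26% flagged.
- No growth, true drug effect of 4 mmHg: 28–31%.
- 2 mmHg/year, no drug effect: 34–37%.

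The drug-effect scenario lies between two growth-only scenarios, so the count alone cannot identify its cause.

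**The case against.** The strongest reply is that this is a descriptive screen and nobody is asked to draw a causal conclusion from it. SAP 2.4.5 plans no systematic testing, and a PCSA is a screening flag rather than a diagnosis. The three-occasion definition sits in the comments column of Appendix A as the basis for the limits, so a one-reading flag is a screening choice and not a contradiction. This stands, and it is why the screen should be kept. It does not supply a summary that a reader could use to judge blood pressure in growing patients.

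Three stronger readings are tempting, and the documents do not support them:
- *Normal growth is reported as drug-related hypertension.* Nothing in the SAP attributes a PCSA to drug.
- *The limits are fixed.* They are reassigned by age band at each visit and also require a rise from baseline. They are fixed only within a band.
- *The randomised comparison is affected.* Placebo patients grow too, and that SAP was not supplied.

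Other handling exists. Hypertension adverse events are tabulated by exposure interval, and the key special-interest tables by age group, gender, pubertal status and weight. Protocol 9.8.1 has a reporting rule needing two consecutive visits, at 160/100 mmHg. Neither gives an age-appropriate rate.

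The magnitude also needs care. The 11 mmHg rise is the step between two multi-year bands. Between assumed midpoints of 9 and 15 years it is 11 / 6 = 1.8 mmHg/year, or about 3.4 mmHg over 96 weeks and 6.7 over 192. The top rows of the table are therefore an upper end.

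On height, Protocol 9.2 restricts measurement to randomization and end of treatment. That matches the double-blind flow chart. The open-label flow-chart footnote lists height with blood pressure and no such limit ("Including systolic and diastolic blood pressure, heart rate, body temperature, weight and height"). Remote visits collect weight only, so they yield no blood pressure to standardise.

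**Conclusion.** The concern holds for the open-label analysis. Blood pressure is summarised only as raw values, raw change from a baseline up to 192 weeks old, and a one-reading PCSA whose limits ignore the sex, height and repeat-reading elements of the definition on which Appendix A bases them. With no control, growth and drug effect cannot be separated in that output. The step to 160/110 mmHg means flags can fall at the 18th birthday with no change in blood pressure.

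In size, 4% to 42% of patients are ever flagged for high SBP with no drug effect under the paediatric limit, or about 2% to 22% with the adult switch. Part of this is noise. For rises of 4 to 8 mmHg, which bracket the 6.7 mmHg estimate, the switched figures are 5–9% (SD 6) and 13–18% (SD 8). All of these depend on the assumed mean, SDs, rise and age distribution, and are illustrations rather than predictions. The fault limits what the report can show about a known effect. It does not make the planned tables wrong.

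**What to change.** In SAP 2.4.5.4, keep the raw tables and the PCSA screen, and add:

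1. A supportive summary restricted to readings taken before age 18, with SBP and DBP expressed as sex-, age- and height-specific z-scores or percentiles from the 2004 paediatric report that Appendix A cites. Use the last height on or before the visit, as SAP 2.5.1 already does for creatinine clearance.
2. Change in z-score by visit, with the number of patients contributing at each visit, because patients leave this summary at 18 and those remaining are younger.
3. A count of patients at or above the 95th percentile on three or more occasions.
4. PCSA counts shown separately before and after the 18th birthday.

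The cost is SAP wording, one derivation and one extra table. Sex, age, height and blood pressure are already collected, but the reference tables must be obtained because they are not in the documents. The drawback is that the standardised summary rests on a shrinking subset. This changes the analysis only; no monitoring or management rule is affected.
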